Maternal Exclusion Criteria

- Active or history of substance use disorder within the past year
- Non-English speaking

Part B:

Maternal Inclusion Criteria

- Subjects enrolled in Part A and willing to consent to Part B of this protocol
- Pregnant with current chronic neuropathic pain
- Subjects failed treatment with amitriptyline or nortriptyline as defined by one of the following:
 - no clinical improvement following a four week trial of amitriptyline or nortriptyline (i.e., CGI-I score ≥ 4)
 - an inability to tolerate the medication (i.e., side effects)
- Subjects must pass the TMS Safety Checklist Adult Safety Screen (TASS).
- Subjects should be off medication, which can lower seizure thresholds (e.g., amitriptyline and nortriptyline) for at least two weeks prior to study entry.
- Subjects with neuropathic pain including those with diagnosis of spinal cord injury, fibromyalgia, compression neuropathies (including diabetic peripheral neuropathy), post stroke pain, and multiple sclerosis
- Subjects with a baseline VAS score greater than 30

Protocol Title: Neuropathic Pain in Pregnancy
Institution: University of Arkansas for Medical Sciences (UAMS)
IRB Number: 204737
Sponsor: UAMS
PI: [name]

Maternal Exclusion Criteria

- Current or past history of a seizure disorder (e.g., epilepsy)
- Current history of preeclampsia
- Current or history of brain lesions (e.g., aneurysm)
- History of major head trauma (e.g., stroke; previous cranial neurosurgery)
- Ferromagnetic metal in the head, neck, or chest (e.g., plates or pins, bullets, shrapnel)
- Microprocessor implants in the head (e.g., cochlear implants) or life-sustaining microprocessor implants anywhere in the body (e.g., prosthetic cardiac valves)
- Cardiac pacemaker
- Active or inactive implants (e.g., deep brain stimulators, vagus nerve stimulators)
- Active treatment with medications that lower seizure threshold (e.g., bupropion, amitriptyline, nortriptyline, or other TCA)
- Increased intracranial pressure (which lowers seizure threshold)
- Implanted medication pumps
- Intracardiac lines
- Significant heart disease defined as heart disease that causes moderate to severe symptoms and/or is characterized by moderate to severe pathology, including a recent history of myocardial infarction and heart failure with an ejection fraction of less than 30% or with a New York Heart Association Functional Classification of Class III or IV.
- Bipolar disorder (to reduce the risk of mania)

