prescription and non-prescription medications used in pregnancy and the postpartum period. A urine drug screen will also be obtained at each visit testing for the presence or absence of the following: amphetamines/methamphetamines, barbiturates, benzodiazepines, THC, cocaine, methadone, opiates, PCP, and cotinine. For all visits following entry visit, subjects will complete the Patients' Global Impression of Change scale (PGIC) (Hurst and Bolton 2004); and the clinician will complete the Clinical Global Impression-Global Improvement scale (CGI-I) (Guy 1976). At all study visits, weight and vital signs will be collected. For all subjects who delivered at UAMS, medical records for labor and delivery and neonatal outcome will be obtained following birth. All subjects will participate in Part A. All subjects will receive treatment as usual within each group.

Part B:

Subjects in group 1 will be invited to participate in part B of the study following their enrollment in part A. This pilot study will aim to enroll 10 subjects (of Group A).

Subjects will undergo daily rTMS, defined as Monday through Friday, for a total of 10 consecutive sessions with the exception of weekends and holidays (i.e., Monday to Friday only). Typically, a stimulation period will start on Monday (day 1) and end on Friday (day 12). In the case that a stimulation period does not start on Monday, day 1 will begin on the day of the subject's first rTMS session. Subjects will be followed daily until day 29, following their last session of rTMS (day 12). Table 2 provides an overview of study procedures. For each session (days 1-5 and 8-12), subjects will complete a VAS prior, immediately following, and 60 minutes post. Adverse events will also be recorded prior to and immediately following and 60 minutes after each session. They will complete a BDI on Days 1, 5, 12, 22, and 29. Subjects will complete VAS also on days 22 and 29. For days 5, 12, 22, and 29; subjects will complete the PGIC; and clinicians will complete the CGI-I. Subjects will have a maximum of 12 visits for Part B (10 rTMS sessions plus days 22 and 29). Either study visit for days 22 or 29 may occur in conjunction with a study visit for Part A.

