- Beck Depression Inventory (BDI) (Part A and B): The BDI is a widely used instrument that has been used in both clinical and non-clinical setting measuring depressive symptoms. It is a 21 item questionnaire with 4-5 responses for each question. Responses are coded 0-3 for the 4 point scales. The 5 point scales include an additional 2a and 2b response code. The symptom categories reflect overt behavioral manifestations of depression. The instrument has both a high degree of reliability and validity (Beck, Ward, Mendelson, Mock & Erbaugh, 1961). This scale will be performed at every subject visit.
- Patient's Global Impression of Change Scale (PGIC) (Part A and B): The PGIC gives a global rating of change in symptoms, activities, emotion, and overall quality of life related to the subject's pain condition. This is a self-rated scale.
- Clinical Global Impression-Global Improvement Scale (CGI-I) (Part A and B): The CGI-I gives a global rating of the improvement/change in the symptoms since the last study visit. This is administered by the MD.
- Visual Analog Scale (Part A and B): 100 mm line scale that is subject administered to subjectively rate current pain symptoms. The subject will be instructed to draw a single vertical line that best describes current state. The VAS will be administered at every subject visit.
- TASS: TASS is the Transcranial magnetic stimulation Adult Safety Screen that is used to alert investigators to factors in potential subjects that may be predisposed to adverse events during rTMS. The decision to proceed with rTMS is entirely up to the investigator's judgment. TASS complements history-taking and is not meant to exclude or replace the investigator's judgment.

Maternal Labs

We will obtain maternal urine collection for research analysis at every subject visit for urine drug screen and cotinine analysis. Urine will be collected and processed in a designated research space at PRI/UWC or in the subject's room in PRI/UAMS and will be sent to an outside laboratory. WMHP research personnel process the research lab. All research samples will be temporarily stored in a dedicated -20 degrees freezers in the Psychiatric Research Institute (PRI) 4th floor laboratory. Access to the samples will be restricted to WMHP research personnel.

Cotinine/Nicotine

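### In Part B the CGI-I is rated against the last study visit, so most ratings do not measure change from the pre-rTMS state, and the reference may differ between subjects

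*Protocol*

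**What the plan says.** The CGI-I entry in the Protocol, Questionnaires and Surveys for Parts A and B, is labelled for both parts and reads: "The CGI-I gives a global rating of the improvement/change in the symptoms since the last study visit". The Investigational Plan, Part B, fixes the rating days: "For days 5, 12, 22, and 29; subjects will complete the PGIC; and clinicians will complete the CGI-I". Table 2 agrees and shows no CGI-I or PGIC on day 1. The same section counts each session as a visit: "Subjects will have a maximum of 12 visits for Part B (10 rTMS sessions plus days 22 and 29". It also allows overlap with Part A: "Either study visit for days 22 or 29 may occur in conjunction with a study visit for Part A".

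For the PGIC the instrument list says "The PGIC gives a global rating of change in symptoms, activities, emotion, and overall quality of life related to the subject's pain condition" and gives no reference point.

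Objective III includes describing the impact of rTMS on neuropathic pain. The Part B (rTMS) statistical text, the same in the Protocol and the SAP, makes VAS primary and BDI, PGIC and CGI-I secondary. For these outcomes it names plots to be read by eye. It sets no other reference for the CGI-I.

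The Part B eligibility criteria use the same scale in another way, to define failure of a tricyclic: "no clinical improvement following a four week trial of amitriptyline or nortriptyline (i.e., CGI-I score ≥ 4".

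**The concern.** A global improvement rating means only what its reference point makes it mean. Objective III calls for a comparison of the subject's state after rTMS with her state before it. A rating against the previous visit instead describes the latest interval, and in Part B that interval can be a single day in the middle of the course. A subject who improved in the first week and stayed improved would be rated unchanged from then on. A subject who improved and then fell back to where she began would be rated worse, although she is no worse than before rTMS.

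Unlike a VAS change, a CGI-I rating cannot be re-scored later against another reference, because the judgement is made once, at the visit. If raters resolve the wording differently, the ratings are also not comparable between subjects.

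**Working it through.** **Inputs.** Monday start (Investigational Plan, Part B): sessions on days 1–5 and 8–12, then visits on days 22 and 29. Visit count: 10 + 2 = 12, which matches the stated maximum and confirms that each session is a visit. CGI-I days: 5, 12, 22 and 29.

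**Step 1: which visit each rating refers to.**

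| CGI-I day | Reading 1: latest earlier visit of any kind | Reading 2: latest earlier visit with a CGI-I |
|---|---|---|
| 5 | day 4 (after 4 sessions) | a Part A visit before rTMS, if one had a CGI-I |
| 12 | day 11 (after 9 sessions) | day 5 |
| 22 | day 12 (after 10 sessions) | day 12 |
| 29 | day 22 | day 22 |

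Reading 1 gives 0 of 4 ratings anchored before rTMS. Reading 2 gives at most 1 of 4. It is at most 1 because Table 1 schedules no CGI-I at Part A entry, so a subject who starts Part B straight after entry has no earlier CGI-I visit.

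**Step 2: shared visits.** Part A visits fall about every 4–6 weeks, that is 28–42 days. Counting back from day 22: 22 − 28 = −6 and 22 − 42 = −20, both before day 1. From day 29: 29 − 28 = 1 and 29 − 42 = −13, so day 1 or earlier. A rater at a shared visit who takes the previous Part A visit as the reference may therefore be looking back to before rTMS. The documents do not say which reference applies there.

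**Step 3: what the ratings would show.** The VAS values here are assumed, purely to illustrate; nothing in the documents maps millimetres onto the CGI-I. Take 60 mm before rTMS, falling 6 mm per session to 30 mm on day 5, and 30 mm through day 12. Then either 30 mm (kept) or 60 mm (relapsed) on days 22 and 29. Rated change is the value on the rating day minus the value at the reference.

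| Path | Measure | Day 5 | Day 12 | Day 22 | Day 29 |
|---|---|---|---|---|---|
| Kept | Reading 1 | 30 − 36 = −6 | 0 | 0 | 0 |
| Kept | Reading 2 | 30 − 60 = −30 | 0 | 0 | 0 |
| Kept | from day 1 pre-session | −30 | −30 | −30 | −30 |
| Relapsed | Reading 1 | −6 | 0 | 60 − 30 = +30 | 0 |
| Relapsed | Reading 2 | −30 | 0 | +30 | 0 |
| Relapsed | from day 1 pre-session | −30 | −30 | 0 | 0 |

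On day 29 both paths show 0 on both readings, while change from day 1 is −30 mm or 0 mm. On day 22 the relapsed subject shows worsening although she is back at her starting level.

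**Step 4: can the ratings be chained?** On Reading 2 the intervals join up: −30 + 0 + 0 + 0 = −30 (kept) and −30 + 0 + 30 + 0 = 0 (relapsed), both correct in millimetres. On Reading 1 they leave gaps (before day 4, and day 5 to day 11): the sums are −6 and +24, against true changes of −30 and 0. The CGI-I is a graded category rather than a length, and the plan gives no rule for combining successive ratings.

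**Step 5: day numbering (minor).** Non-Monday starts are allowed: "In the case that a stimulation period does not start on Monday, day 1 will begin on the day of the subject's first rTMS session". With weekends off and no holidays, session 10 falls on day 12 for a Monday start and on day 14 for a Tuesday, Wednesday, Thursday or Friday start. For example, a Tuesday start gives sessions on days 1–4, 7–11 and 14. On Tuesday and Wednesday starts, days 5 and 12 fall on a weekend, when no session is held.

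**The case against.** The best case on the other side has four parts.

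- **One descriptive sentence.** The point rests on a summary of the instrument. The rating forms are not in the documents and may print their own anchor. Starting CGI-I and PGIC on day 5, while BDI starts on day 1, fits a day 1 reference, and so does the eligibility rule that applies the CGI-I to a whole four-week drug trial. These are indications only. The one explicit rule says otherwise and is labelled for Part B. The eligibility wording fits poorly with it, and that tension is a reason to reconcile the two.
- **Shared visits.** A reader might infer that Part B CGI-I ratings never have a pre-rTMS reference. The documents do not support that: a visit shared with Part A could carry one. This part stands. What remains is an anchor that is mostly not before rTMS and may vary.
- **The course is not wholly lost.** In the illustration, day 22 separates the two subjects on both readings, and on Reading 2 the intervals are contiguous. This stands too. The path is constructed: with further improvement in week 2, Reading 2 would show change at day 12. The claim is about what a single rating means.
- **Small stakes.** The CGI-I is secondary in a single-arm pilot of 10, and VAS and BDI give change from day 1 directly. This limits the weight of the point but does not remove it, because the correction costs almost nothing.

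**Conclusion.** The point holds in a limited form. Followed as written on a Monday start, 0 of 4 Part B CGI-I ratings (any visit) or at most 1 of 4 (last CGI-I visit) are anchored before rTMS. The exception is a day 22 or 29 visit shared with Part A, where the reference is ambiguous. Single ratings therefore do not describe change from the pre-rTMS state, and the anchor could differ between subjects. The counts rest only on the schedule and the stated definition; the millimetre figures rest on assumed VAS values.

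A reader might go further and infer that the impact of rTMS cannot be assessed, or that the VAS analysis is wrong. Neither follows. VAS has up to 10 × 3 + 2 = 32 readings per subject, including one before the first session, and BDI is taken on day 1, so change from baseline can be computed under the plan. That the change is not defined in advance is missing detail. The PGIC reference and the day numbering are likewise clarifications, not errors in the results.

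**What to change.** **Main change.** For Part B, rate the CGI-I against the day 1 pre-session state and give the PGIC the same reference. At a visit shared with Part A, record the Part A and Part B CGI-I separately. Reconcile the instrument description with the way the Part B eligibility criteria use the scale. The cost is one reference line on each of two forms and one extra CGI-I rating at shared visits. No visits are added.

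**Minor clarifications.**

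- Besides the plots, report change in VAS (from day 1 pre-session) and BDI (from day 1) to the end of the course, day 22 and day 29, with the SD of change and a 95% CI. Say which post-session VAS reading is used, immediate or 60-minute, and describe the estimates as uncontrolled. With n = 10 the half-width is t(0.975, 9)/√10 = 0.715 times the SD of change. If that SD is 20–30 mm (an assumption), this is 0.715 × 20 = 14.3 mm to 0.715 × 30 = 21.5 mm, so the estimates will be imprecise. The cost is one SAP sentence and no new data.
- Tie the ratings labelled day 5 and day 12 to sessions 5 and 10.
- The sentence "Subjects will be followed daily until day 29, following their last session of rTMS (day 12" does not fit the 12-visit maximum, and its day 12 holds only for a Monday start. The passages must be reconciled.

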To further define the impact of NP in the peripartum period, we propose the following objectives:

- I. Characterize the course and pharmacological management of neuropathic pain in pregnancy and the postpartum period. We will define descriptive statistics of the use of analgesic medications in pregnancy and the postpartum period for the treatment of neuropathic pain.
- II. Compare obstetrical and neonatal outcomes of pregnant women with chronic neuropathic pain, non-neuropathic chronic pain, and pregnant women without chronic pain.
- III. Determine the acceptability and tolerability of rTMS for the treatment of neuropathic pain in pregnancy, and describe the impact of rTMS on neuropathic pain in pregnancy.

Subject Selection

Subjects will be enrolled through the Women's Mental Health Program (WMHP) at the University of Arkansas for Medical Sciences (UAMS) at the following clinical spaces: Psychiatric Research Institute (PRI); UAMS Women's Clinic (UWC); the Psychiatric Research Institute (PRI) inpatient units (PRI floors 5&6); and the UAMS Obstetrics & Gynecology units (UAMS floors 5,6, and 7A).

Protocol Title: Neuropathic Pain in Pregnancy
Institution: University of Arkansas for Medical Sciences (UAMS)
IRB Number: 204737
Sponsor: UAMS
PI: [name]

Study visits can occur at all of the above locations. For those subjects in part B, study visits will occur in a designated room designed for rTMS in the PRI. We aim to actively recruit and enroll 60 pregnant women and up to 70 infants (to allow for multiple gestation pregnancies) for Part A of this study and enroll 10 pregnant women and up to 15 infants (to allow from multiple gestation pregnancies) (from Part A) for Part B.

Compensation: Mothers participating in the study will receive a \$10 in cash for each visit. All participants will be given a token or voucher to pay for parking at each outpatient study visit when applicable.

Inclusion of Women, Minorities and Children

Women and adolescents between 18-45 years of age are eligible for participation in the current study. Every effort will be made to recruit a diverse population of women along racial and ethnic categories residing in underserved areas.

Eligibility Criteria

All women will provide consent and HIPAA authorization prior to enrollment in the study.

Part A:

Maternal Inclusion Criteria

- Age 18-45 years old,
- Ability to give informed consent,
- Viable pregnancy, and
- Enrollment prior to or equal to 24 weeks gestation

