Subjects will be identified by clinical staff based on current pregnancy status to identify potential subjects for the study. Once referred, initial screening by research personnel will include reviewing inclusion and exclusion criteria (as described in Eligibility Criteria) discussing the study, obtaining informed consent, completing the TASS questionnaire and initiating enrollment. These assessments and health related information will be collected on a paper form. All personnel will be qualified to administer all questionnaires.

Access to Medical Records: As a part of the informed consent for this protocol, individuals will allow the investigative team access to medical records. Any information acquired from medical records will be de-identified (no PHI, only subject ID code) and stored with the de-identified records obtained for this study.

The medical record will be utilized to gather obstetrical information regarding gestation and delivery of the infant, which may include but not limited to infant weight, height, APGAR scores, gender, head circumference, method of delivery and maternal or infant complications. Collection of health information will occur shortly following delivery of infant. Infants will only be assessed via medical records. There will be no direct assessment of infants within the scope of this study.

Questionnaires and Surveys for Parts A and B:

- Pain Interference Scale-Short Form 4a (Part A): This 4-item self-report scale measures the consequences of pain on relevant aspects of the subject's life. It includes impairment in the subject's social, cognitive, emotional, physical, and recreational activities. It also incorporates items about sleep and enjoyment of life. The short form is not disease specific and assesses pain interference over the past 7 days.
- Pain Behavior Scale-Short Form 7a (Part A): This 7-item, self-report scale measures behaviors that typically indicate to others that an individual is experiencing pain. These measures include observations (sighing, crying), behaviors (resting, guarding, facial expressions, asking for help), and verbal reports of pain. The short form is not disease specific and assesses pain interference over the past 7 days.

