minimize obstetrical complications. Our experience has been that with effective education and supportive interactions, the majority of women will inform both their obstetrical and pediatric care providers. In the event that the subject refuses to notify their obstetrical care provider, this is viewed as a potential hazard to the pregnancy and infant, and in the opinion of the investigative team constitutes a 'duty to warn' – since the fetus cannot be warned, the subject will be asked to meet to discuss how to best inform their obstetrical care provider. The details regarding how to handle such medication use in pregnancy is not covered under the auspices of the social service offices in the Little Rock area. The subject's obstetrical care provider will be notified by phone with the subject in the office to permit them to hear how the information is communicated. If the subject declines such a meeting, the obstetrical care provider will be notified. The study investigators are experienced with the treatment of substance abuse in pregnancy, and the study participants will be offered care for their substance abuse problem. Given the importance of providing these women optimal clinical care, we have found that having an office visit to discuss the results and treatment planning, as well as making contact with their obstetrical care provider in their presence has been remarkably successful at keeping the women engaged in care.

Statistical Methods and Data Management

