Abuse of illicit or licit substances during pregnancy poses a potential risk to the subject and their pregnancy that their obstetrical and pediatric care provider should be aware. As a policy, we strongly encourage subjects to communicate this information to their obstetrical and pediatric care providers. We will only share this information with other care providers with subject's signed release of information. To the best of our knowledge, participation in part A of this study poses no risk to pregnancy and/or the infant. There may be risks, discomforts, or side effects that are not known yet. There is also the possibility of loss of confidentiality.

Risks Associated with Part A

No real risks are associated with Part A of this study other than possible loss of confidentiality. Subjects may decline to answer any questions that may make subjects uncomfortable.

Risks Associated with rTMS (Part B)

Likely: Subjects may feel anxious about participation. This typically abates after the first one or two sessions.

Less likely: Subjects may experience minor discomfort associated with head and hand muscle twitching, headache, local (head and neck), and dental pain. Head and neck pain related to stimulation of underlying muscle and nerves occurs in approximately 10% of subjects. The incidence and severity is a function of stimulus site and intensity but is most common over frontal-temporal regions. The symptoms are typically mild and limited to the time of stimulation and can be treated with acetaminophen if necessary. Subjects typically tolerate the discomfort better as session's progress. The coil position is adjusted if pain occurs. Subjects will be advised to take acetaminophen for treatment if necessary. The study physician or nurse will monitor subjects during and after each rTMS for twitching of a hand muscle, such as the abductor pollicis brevis or the first dorsal interosseous muscle, on the side of the body that is contralateral to the rTMS treatment site.

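### On the more natural reading, the promise to share substance-abuse information only with a signed release conflicts with the procedure for notifying the obstetrical provider when a woman refuses to disclose

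*Protocol*

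**What the plan says.** Two parts of the protocol deal with substance use that a woman has not told her obstetrical provider about.

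**Maternal Labs, Illicit Drugs.** The section covers undisclosed prescription medication, medication from other sources, and illicit substances. Education and support come first, and the investigators report that most women then inform their providers. If a woman refuses, they regard this as a hazard to the pregnancy and infant that creates a duty to warn, and she is asked to a meeting. "The subject's obstetrical care provider will be notified by phone with the subject in the office". If she will not attend: "If the subject declines such a meeting, the obstetrical care provider will be notified". The section also says that "the study participants will be offered care for their substance abuse problem", so the procedure reaches use that amounts to abuse.

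**Risks and Benefits, the paragraph before Risks Associated with Part A.** This concerns abuse of illicit or licit substances in pregnancy. It says that the obstetrical and pediatric providers ought to know, and continues: "As a policy, we strongly encourage subjects to communicate this information to their obstetrical and pediatric care providers". The next sentence is: "We will only share this information with other care providers with subject's signed release of information".

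Three other statements bear on the point. Eligibility Criteria: "All women will provide consent and HIPAA authorization prior to enrollment in the study". Initial Screening, Access to Medical Records: "As a part of the informed consent for this protocol, individuals will allow the investigative team access to medical records". Risks Associated with Part A: "No real risks are associated with Part A of this study other than possible loss of confidentiality". The SAP is silent on disclosure.

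**The concern.** One text tells staff to notify the obstetrical provider over a woman's refusal. The other appears to tell them to share nothing without her signature. The protocol does not say which prevails, so staff working from different pages could treat two women in the same position differently.

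This is a participant-protection matter. Telling a provider about drug use in pregnancy against a woman's wishes cannot be undone. A woman who has been given the signed-release statement would reasonably not expect it. The Part A risk text mentions a possible loss of confidentiality, but a planned notification without agreement is a different thing, and that text does not describe it.

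**Working it through.** No arithmetic applies. The check sets the two rules side by side and asks when they collide.

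| | Illicit Drugs | Risks and Benefits |
|---|---|---|
| Scope | Undisclosed medication and illicit substances, including abuse | Abuse of illicit or licit substances |
| First step | Education and support | Encouragement to tell the providers |
| If she refuses | Team notifies the obstetrical provider | Not stated |
| Condition on the team's sharing | None stated | Signed release only |
| Exception or cross-reference | None | None |

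**Step 1: do the scopes overlap?** Yes, for substance abuse. The Illicit Drugs procedure is wider, because it also covers ordinary medication that a woman has not mentioned. For that use the release sentence does not apply and nothing conflicts.

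**Step 2: does the release sentence reach the obstetrical provider?** This turns on *other care providers*.
- Reading A: any provider outside the study team. The paragraph names the obstetrical and pediatric providers, leaves telling them to the woman, and then limits what the team itself may share. In that sequence, *other* contrasts with the study team.
- Reading B: providers besides the obstetrical and pediatric ones just named. The release rule then leaves the obstetrical provider out and there is no strict contradiction. But the sentence would govern providers whom the paragraph never otherwise mentions, and would say nothing about the team's sharing with the two it has just discussed.

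Reading A is the more natural, but the wording does not exclude B.

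**Step 3: what happens under Reading A?** Take a woman whose use is abuse, who refuses to disclose, and who has signed nothing that covers her obstetrical provider. The Illicit Drugs section requires notification and the release sentence forbids it. The collision is sharpest when she declines the meeting, because that route contains no step at which a release might be signed.

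**Step 4: does other text settle it?** The authorization signed before enrollment could cover the obstetrical provider, but its content is not available for review. The records-access statement describes information coming in to the team, so it neither shows nor rules out a release for information going out. The Cotinine/Nicotine section states plainly that obstetricians will not be told of a positive result. It shows that the protocol can write a provider-specific rule when it means one, but it does not govern this case.

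**Step 5: how often?** Part A excludes women with a current substance use disorder or one in the preceding year, and the investigators report that most women disclose. No refusal rate is given, so the number cannot be estimated.

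**The case against.** The best counter-argument is that there is no conflict. The obstetrical and pediatric providers are named in the two sentences before the release sentence, and *other*, coming after a named class, can well mean those outside it. Encouragement is also the first step in the Illicit Drugs section, so the risk paragraph may simply describe the opening of the same staged procedure and be silent on refusal. The Illicit Drugs text is the detailed operating procedure, and staff might be expected to follow it over a short policy statement. Finally, the enrollment authorization may already cover the provider.

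Much of this stands as possibility. It is why the point is tied to one reading and to women without a covering authorization. It does not remove the need for a repair: nothing marks the Illicit Drugs text as an exception, the release sentence says *only*, and even under Reading B the risk paragraph describes encouragement where the procedure requires notification.

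Some stronger inferences are tempting but unsupported:
- *That the protocol certainly contradicts itself.* Reading B and the unseen authorization prevent that claim.
- *That women are not told of the notification.* The consent wording is not available for review, so this is something to check and not an established omission.
- *That every positive drug screen leads to a report.* Notification follows refusal to disclose, not the screen result.
- *That the release rule should prevail.* The documents do not say so. Making notification depend on a release would reverse the investigators' stated position and leave their duty-to-warn sentence standing against it.

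**Conclusion.** The point holds with moderate confidence. On the more natural reading, the signed-release promise and the notification procedure are incompatible for a narrow group of women: those whose use counts as abuse, who refuse to disclose, and whose authorization does not cover the obstetrical provider. The conclusion assumes that *other care providers* includes the obstetrical provider and that the authorization does not already settle the matter; if either assumption fails, the strict conflict goes and an unclear text remains. Few of the 60 women planned for Part A are likely to be affected. No endpoint, sample size or analysis depends on it. It should still be corrected, because the harm from a mistaken disclosure is irreversible and the correction is small.

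**What to change.** Keep the Illicit Drugs section as the operating procedure, and bring the rest into line with it:

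1. In the signed-release sentence, replace *other care providers* with the providers actually meant, and add: *except as described under Illicit Drugs, where the obstetrical provider will be notified if the subject declines to do so*.
2. Under Risks Associated with Part A, list this planned notification as a specific risk, separate from accidental loss of confidentiality.
3. Confirm that the consent and HIPAA wording states it, and that each woman has seen it before her first urine sample.

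The cost is one IRB amendment, with no change to visits, sample size or analysis. The drawback is a less reassuring confidentiality statement, which might make some women less willing to enroll or to report use. That is the price of describing accurately what the investigators intend to do.
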